**4.0 Rockefeller University Conflict of Interest**

- 4.1 Investigator Financial Conflict of Interest**  
**All KSP (unless they have done so in the past 12 months) must complete and update promptly a Rockefeller University Significant Financial Interest Disclosure at <http://mycoi.rockefeller.edu/>. Prompt disclosure means within 30 days of discovering or acquiring a Significant Financial Interest, and as early as possible in the development of this protocol. If a KSP discloses a significant financial interest that may constitute a conflict of interest with respect to the proposed study, he or she must E-mail a copy of the Lay Summary of the study to [name] ([[contact]](mailto:[contact])). Doing so will allow the process of addressing the potential COI to proceed in step with the development of the study protocol. Tardiness or non-compliance with this requirement will very likely cause delay in submission of the study for IRB review.**
- Institutional Conflict of Interest**  
**As early as possible the PI or designee preparing this application must log in to <https://icoi.rockefeller.edu/account/login.php>, which lists entities in which The Rockefeller University has a direct financial interest. If the proposed study involves any entity on that list the PI or designee must E-mail the entity involved and a copy of the Lay Summary to [name] so that the process of addressing the potential Institutional COI can proceed in step with the development of the study protocol.**

**Add up to three additional authorized activities specific to this study:**

31: Adverse Event assessment

32:

33:

**Activity Codes Continued:**

- 34. Behavioral Testing
- 35. Bod Pod
- 36. Bone Marrow Aspiration
- 37. Neuropsychological Testing
- 38. Conduct Focus Group
- 39. Conduct Smell Study
- 40. Genetic Counseling
- 41. Apply EEG Electrodes
- 42. Olfactometer Test
- 43. Study Participant Teaching
- 44. Resting Energy Expenditure
- 45. Source Document Review & Correction
- 46. Medical Photography
- 47. Write/Sign LIP orders

## 7.0 Study Description

### 7.1 \* Lay Summary

Please provide a summary of your study in lay language. The summary should be no more than a half page (500 words or less) and should contain a clear statement of the rationale for the study.

The development of industrialization with increased food consumption and sedentary has given rise to an obesity pandemic, which affects up to 30% of the population in countries like US, these populations being at greater risk for cardiovascular diseases, and diabetes. More than obesity per se, visceral obesity is associated with metabolic diseases (1) that cluster together and clinically defined metabolic syndrome (MetS). MetS comprises individuals with at least three of the 5 of the following factors: abdominal obesity, high blood triglycerides, low HDL ("good cholesterol"), high blood pressure and elevated fasting glucose (2). Metabolic syndrome is associated with a low-grade inflammation or metaflammation characterized by an infiltration of immune cells particularly in the adipose tissue, the liver and the pancreas (3) that is thought to be responsible for the induction of insulin resistance. It is thought that obesity predisposes to other diseases such as cancer, asthma but only little attention has been given to infectious diseases (4, 5). Studies have shown that obesity increases the risk of severe influenza infection (6) and associated death and reduces the efficacy of influenza vaccine in the obese population (7) but yet, the molecular mechanisms have not been described. Immune dysfunctions associated with obesity are suspected to play a major role but obesity is often associated with respiratory disorders that could directly explain the increased susceptibility to influenza infection (8). Also, metabolically healthy obesity is less associated with metaflammation (9). Therefore, we would like to focus particularly on metabolic syndrome, and determine how it influences immune response to viruses. We are thus hypothesizing that differences in the innate immune responses between individual with or without metabolic syndrome impact viral infection and vaccine outcome. Recent studies involving complex biological analysis and computational modeling have shown that the ability of an individual to positively respond to influenza vaccine can be molecularly predicted by looking at markers in the blood cells (10-12). We will perform seasonal influenza vaccination in people with or without metabolic syndrome to determine if the late adaptive response assessed by antibodies titers is different between the two groups and correlates with the early immune response assessed by gene expression profile in whole blood cells. Healthy nutritional habits along with increased physical activities should be best at preventing the development of metabolic syndrome but socio-economical issues are slowing the implementation of these changes. Therefore, as metabolic syndrome is raising public health concerns, it is important to understand why the metabolic syndrome affects susceptibility to diseases. The project we propose will contribute to a better understanding of the inflammatory phenotype associated with metabolic syndrome and establish for the first time if it affects the immune protection against infectious diseases and particularly against influenza virus infection. Our results are important to determine if the population affected by metabolic syndrome should receive anti-influenza treatment in priority in the context of a severe influenza epidemic.

### 7.2

#### \* Public Health Impact Statement

Provide a brief plain language statement (100 words or less) of the value of the research proposed and its potential impact on population health. Additional instructions located in Help.

Metabolic syndrome (MetS) is the combination of unhealthy metabolic factors associated with obesity that confer an increased risk for cardiovascular disease and diabetes. Influenza vaccine has been shown to be less protective in obese individuals without assessment of their metabolic status. We would like to study the influenza vaccine response in people with and without MetS. We believe our study might help develop vaccines of better efficacy for this population and understand immune deficiencies associated with metabolic syndrome and obesity.

**7.3**

**\* Submission Request Category**

Please indicate:  
Full Review

**8.0**

**Clinical Trial Registration**

**8.1**

**Clinical Trial Registration**

The types of studies listed below must be registered at [www.ClinicalTrials.gov](http://www.ClinicalTrials.gov) /> **before enrolling the first participant in order to be in compliance with federal regulations and preserve the opportunity to publish the study in journals that adhere to the ICMJE guidelines. Please check the answer that best applies.**

- Study involves testing of FDA regulated drugs or biologics (See HELP)
- Study is funded by the NIH, and meets the definition of a "clinical trial" (see HELP)
- Study meets the ICMJE definition of a "clinical trial" (See HELP)
- None of the above

If you selected 1, 2, or 3, you must register your trial with ClinicalTrials.gov through the Rockefeller University institutional account. Please contact the Clinical Research Support Office [name] for assistance.

**9.0**

**Study Overview/Summary**

**9.1 \* Who initiated this study?**

Please specify one:

- Principal Investigator Initiated
- Industry Initiated
- Other

If other, please specify:

**9.2 \* This study in collaboration with:**

- Weill Cornell Medical College
- Memorial Sloan-Kettering Cancer Center
- Both Weill Cornell Medical College and Memorial Sloan-Kettering Cancer Center
- Neither Weill Cornell Medical College nor Memorial Sloan-Kettering Cancer Center

Please note: If any of the first three options is checked, you will be prompted to attach the **Tri-Institutional Study Specific Financial Disclosure** and the **IRB of Record** forms later on in the submission. Links to these forms can be found in the Help link to the right.

**9.3 \* Are other institutions involved in the study?**

- 1. No
- 2. Yes, and a federal, industry or private organization is administratively coordinating the study.
- 3. Yes, however, a federal, industry or private organization is not administratively coordinating the study.

If #3 was selected above, please provide the following for each involved institution:

Name of Other Institution	Date of Approval by Other Institution	Date of Pending Approval by Other Institution	Date of Expiration at Other Institution

No records have been added

**9.4 \* Is this a multi-center trial?** Yes  No**9.5 \* Who (What) is to be studied?**

- Human Subjects - including coded samples and/or data with links to Identifiers  
 Deidentified Samples - unable to be linked to identifiers by receiver  
 Data Only - unable to be linked to identifiers

**9.6 \*Study Type:**

- Interventional  
 Observational

**9.7 The initial date of IRB approval was:**

11/25/2015

**9.8 \* What is the expected duration of the study?**

3 years

**9.9 \* Are any of the following agents to be used in the study?**

Check all that apply:

- Drug FDA Approved  
 Approved Drug for Off-Label Purpose  
 Investigational New Drug  
 Biologic Agents  
 Nutritional Supplements  
 Placebo  
 Vaccines  
 No Agents

**9.10 \* Are investigational devices to be used in the study?** Yes  No

If Yes, please specify:

- A Significant Risk Device  
 A Non-significant Risk Device

**9.11 Special Research Procedures**

Does the study propose to directly involve participants in the following special research procedures?

- Recombinant DNA  
 Gene Therapy

If either item is checked, please see Help for details.

**9.12 \* Radioactive Isotopes Involved**

Will subjects be exposed to any radiation other than routine x-rays solely for clinical care purposes?

 Yes  No

**10.0 Interventional****10.1 \*Interventional, please specify:**

- Open Label  
 Single Blind  
 Double Blind  
 Other

If Other, specify:

All participants seen at RU will receive the flu vaccination.

**11.0 Objectives and Rationale****11.1 \* Overview**

Briefly state the *purpose of this study*. Give enough background and rationale to provide both scientists and lay members of the IRB and ACCTS with the basis for exposing human subjects to the risks involved.

Metabolic syndrome is associated with a chronic inflammatory state that is thought to be determinant in the development of diabetes and cardiovascular events. Excess energy intake results in a hypertrophy of the adipose tissue that generates the production of pro-inflammatory molecules like TNF alpha, and IL-6, which turn on the immune response. This results in infiltration of immune cells like macrophages and natural-killer (NK) cells in the adipose tissue. As oppose to inflammation triggered by a pathogen, chronic inflammation or metaflammation induced in the context of excess nutrient intake does not resolve and directly leads to a decrease of insulin sensitivity. As energy imbalance persists and metabolic syndrome progresses, not only the adipose tissue, but also the liver, the pancreas, and the muscles are sites of inflammation and insulin resistance (3). The role of key immune molecules, such as pathogen sensors like toll-like receptors (TLR) in metabolic syndrome and obesity has been demonstrated by showing that their ablation in mice conferred protection against insulin resistance (13). Thus, classical pathways of inflammation used to activate the immune system in the context of an infection are primed in the context of metaflammation. This leads us to speculate that these pathways might be altered and less prone to react in the event of an infection (3).

To support our hypothesis, several studies have demonstrated that during the 2009 influenza H1N1 pandemic, obesity was associated with more severe infection and death (6, 14). The mechanism is likely immune mediated but has not been determined yet (15). Also, it has been reported that obese people might be less protected by influenza vaccination (7). The area of systems biology has considerably contributed to a better understanding of vaccine efficacy (10, 16). Gene expression studies using peripheral blood can predict vaccine response to influenza (10, 11). High vaccine response correlates with the expression of interferon signaling (genes like STAT1, IRF9) and antigen processing and presentation. To test our hypothesis, we contacted the authors of a study published in Cell in 2014 (12) and obtained the BMI of the patients. The study demonstrated the ability to predict the influenza vaccine response using several parameters. We focused on the immune response based on antibody titers and the gene expression profile at D0 and D1. We separated the individuals in 2 groups: one group of lean (BMI<25) and one group overweight and obese (BMI>25). The two groups contained 25 and 17 individuals respectively. We observed a trend towards an inverse correlation of the immune response to influenza vaccine with increasing BMI. Also, we analyzed the differential gene expression profile between D0 and D1 between the two groups. JUN Kinase, Stat1 and IRF1 were among the most up-regulated genes in the lean group but not in the overweight and obese group. When comparing the two groups using ingenuity pathway analysis, the role of PKR in interferon response, Toll like receptor signaling, Natural killer cell signaling were more activated in the lean group compare to the overweight and obese group. These results indicated that the innate immune response induced by the vaccine might be attenuated in the overweight and obese group. BMI was the only factor used for this analysis and we did not have access to any metabolic marker. Obesity is not necessarily associated with an unhealthy metabolic status. Therefore, we would now like to focus on metabolic syndrome as it better correlate with an unhealthy metabolic status. Our aim is to determine if metabolic syndrome attenuates the immune protection induced by the vaccine and establish the molecular mechanism of antiviral immune deficiency associated with metabolic syndrome. We would like to know if differences between people with and without metabolic syndrome can be seen at the molecular level and correlate with differences in antibody titers. We believe our study will contribute to 1/ better understand vaccine efficacy 2/ establish if the low-grade chronic inflammation associated with metabolic syndrome impacts the systemic immunity against viral infection.

**11.3 \* Hypothesis**

Describe the *research hypothesis* in a single sentence.

We are hypothezing that immune dysregulation associated with obesity and metabolic syndrome affect the influenza vaccine immune response putting these populations at risk for a more severe infection outcome.

**11.4 \* Aim(s)**

Indicate how you will *address the hypothesis* (e.g., to compare groups, to estimate a parameter, to ascertain feasibility). Since the sample size determination is usually based on the primary aim only, the primary aim should be sufficient to justify the study.

Antibody response post influenza vaccine will be compared between subjects with the metabolic syndrome and healthy lean controls

**11.5 \* Primary Outcome(s)**

Indicate which *variable(s)* will be assessed to judge the primary specific aim. Give measurement units, if applicable.

Antibody titers and vaccine response (hemagglutinin)

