**STUDY VISIT #4 (Day 28 +/- 2 days)**

Labs: gene expression - (3) 2.5ml Pax RNA tubes. (total 7.5ml)

Influenza A & B antibodies - (1) 10ml red top tube

Research Blood: Cytokines (9ml for plasma (purple EDTA tube), 10ml for serum (red top tube)

Total blood volume to be drawn for study visit #4 = 36.5ml)

Adverse event assessment

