**STUDY VISIT #6 (Day 90 +/- 7 days)**

Labs: gene expression (3) 2.5ml Pax RNA tubes. (total 7.5ml)

Influenza A & B antibodies - (1) 10ml red top tube

Research Blood: Cytokines (9ml for plasma (purple EDTA tube), 10ml for serum (red top tube)

Total blood volume for study visit #6 = 36.5ml

Adverse event assessment

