**RESEARCH LABS**

**Analyze blood sample and serum for evaluation of the immune response to influenza:****1/ Hemagglutination inhibition assay**

Determine antibody titers against each strain of influenza included in the quadrivalent 2016-2017 vaccine: A/California/7/2009 (H1N1); A/Hong Kong/4801/2014 (H3N2); B/Brisbane/60/2008(B/Victoria lineage); B/Phuket/3073/2013 (B/Yamagata lineage) as described in similar studies (10, 11).

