**11.8 \* Data Analysis**

Describe method(s) of data analysis. Include the role of external collaborators as appropriate.

As per recommended by the food and drug administration (17), the hemagglutination inhibition (HI) antibody assay has been used to assess vaccine activity and may be appropriate for the evaluation of the pandemic influenza vaccine. Appropriate endpoints may include: 1) the percentage of subjects achieving an HI antibody titer  $\geq 1:40$ , and 2) rates of seroconversion, defined as the percentage of subjects with either a pre-vaccination HI titer  $< 1:10$  and a post vaccination HI titer  $> 1:40$  or a pre-vaccination HI titer  $\geq 1:10$  and a minimum four-fold rise in post-vaccination HI antibody titer. Previous study have built models using both HAI and neutralization assays to determine vaccine responsiveness.

The RNA-seq analysis will be run with the help of the Genome resource center as well as the expertise of [name] listed as a collaborator of this project.

**11.9 \* Explain the rationale for the choice of statistical measures and the number of subjects proposed for the study, including the power calculations when applicable.**

Since no preliminary data is available to estimate the percentage of participants achieving a determined level for the HI antibody titer and the rate of seroconversion for each group (healthy volunteers and metabolic syndrome participants) we provide an estimation of the minimum effect size for the sample size selected is able to detect. For a sample size of 40 participants, 20 at each group, a 95% significant Chi-square test will be able to detect an effect size equal or larger than 0.56 with 0.8 power. It means that a Chi-square test will be able to detect independence between groups if the distance between the observed odd ratio is larger than 1.56.

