**Statistical Analysis**

To compare the means of antibody titers between groups (healthy volunteers and metabolic syndrome participants) a t-test at 95% significance level will be performed if the data follows a normal distribution, otherwise a non parametric Wilcoxon-Mann-Whitney test will be used.

A Chi-square test at 95% significance level will be used for the comparison of percentage of participants achieving a determined level for the HI antibody titer and rates of seroconversion. On that case if any observed frequency is smaller than 5 Fisher exact test will be used instead of Chi-square.

Expression values will be modeled using mixed-effect models, with group as fixed factor, and a random effect for each participant. FCHs for the comparisons will be estimated, and hypothesis testing conducted.

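### The primary outcome is not reduced to one comparison: up to 24 tests at the 5% level fit the text, with no deciding test and no error control

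*Combined protocol and SAP*

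**What the plan says.** The primary aim (11.4) is stated as "Antibody response post influenza vaccine will be compared between subjects with the metabolic syndrome and healthy lean controls". It names no time point and no strain. The primary outcome (11.5) is "Antibody titers and vaccine response (hemagglutinin", again without strain, visit, summary measure or unit.

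The rest has to be pieced together:

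- **Strains.** Under Research Labs in 11.7 the HI assay is to "Determine antibody titers against each strain of influenza included in the quadrivalent 2016-2017 vaccine", which lists four.
- **Visits.** After vaccination, blood labelled for influenza antibodies is drawn at "STUDY VISIT #4 (Day 28 +/- 2 days") and again at Study Visit #6 (Day 90), where the entry reads "Influenza A & B antibodies - (1) 10ml red top tube".
- **Endpoints.** Section 11.8 offers two responder measures as possible endpoints: "the percentage of subjects achieving an HI antibody titer" of at least 1:40, and "rates of seroconversion, defined as the percentage of subjects with either a pre-vaccination HI titer" below 1:10 with a post-vaccination rise, or a four-fold rise from a higher start.
- **Tests.** The Statistical Analysis text under 11.9 begins "To compare the means of antibody titers between groups", by t-test or Wilcoxon. It then sets chi-square or Fisher tests for both responder measures. Both kinds of test are at the 5% level; sidedness is not stated.

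No readable section gives a hierarchy, a composite across strains, a deciding visit or a multiplicity adjustment. The text between sections 11.1 and 11.3 was not available for this check.

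**The concern.** A primary outcome should lead to one identifiable result that settles the primary aim. Here strain, endpoint and visit are all left open, so several results could each be presented as the primary one, and the choice could be made after the data are seen. The 5% level then applies to each test taken alone, not to the trial's main claim that metabolic syndrome weakens the vaccine response. That claim carries weight: the lay summary (7.1) says the results matter for deciding whether this population should have priority for anti-influenza treatment in a severe epidemic.

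**Working it through.** **The plan's own figure.** The documents state no overall false-positive rate, so there is none to reproduce. The only design figure is the detectable effect in 11.9: 0.56 for a single chi-square test with 40 participants at 80% power. It does not reproduce. With one degree of freedom and a 5% level, the detectable Cohen's w is 0.443, and w = 0.56 would have 94% power. This is a separate defect. It matters here only because the figure must be restated once a primary test is chosen.

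**Counting the tests.** 4 strains (Research Labs) × 3 HI endpoints (11.8 and Statistical Analysis) × 2 post-vaccination visits (Study Visits #4 and #6) = 24. Day 28 alone gives 4 × 3 = 12. Day 28 mean titre alone gives 4. Neutralization is left out because 11.5 names hemagglutinin; including it would enlarge the set.

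**Reference values under independence.** The chance of at least one p < 0.05 among k tests is 1 − 0.95^k:

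- k = 4: 1 − 0.8145 = 18.5%
- k = 12: 1 − 0.5404 = 46.0%
- k = 24: 1 − 0.2920 = 70.8%

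**Allowing for correlation.** The tests share participants, so these values are too high for the larger sets. A simulation with no group difference used 20 per group (11.9), HI titres on a two-fold dilution scale, t-test or Wilcoxon for titres, the plan's rule of Fisher when any observed count is below 5, and 4,000 runs per setting. The documents give no correlations or titre distributions, so these were assumed: between-strain correlation 0 to 0.8, Day 28 to Day 90 correlation 0.6 to 0.95, and several titre levels. Two-sided tests were assumed. The middle setting has correlations 0.4 and 0.8.

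| Set of tests | k | Independent | Middle setting (Wilcoxon) | Range |
|---|---|---|---|---|
| Day 28 mean titre | 4 | 18.5% | 16% | 12–19% |
| All Day 28 | 12 | 46% | 26% | 20–30% |
| Day 28 and Day 90 | 24 | 71% | 40% | 27–50% |

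With the t-test, the middle value for 24 tests is 43%. The simulation standard error near 40% is √(0.4 × 0.6 / 4000) = 0.8 percentage points; near 18.5% it is 0.6 points, which explains why the top of the first range slightly exceeds its independence value. In the middle setting each titre test rejected about 4.6% of the time and each proportion test about 3.3%, because the small-count tests are conservative. That also holds the totals below the independence values. A 40% rate corresponds to ln(0.60)/ln(0.95) ≈ 10 independent tests.

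**After a fix.** One pre-specified test has a 5% error rate by construction. Bonferroni over 24 (0.05/24 = 0.0021 per test) gave 1.4–2.7% overall, so it controls error but is conservative.

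**The case against.** The strongest reply is that the plan never commits to 24 tests. Research Labs describes measurement per strain, not testing per strain. The Statistical Analysis text does not say its tests are run by strain or by visit. Section 11.8 introduces the responder measures only as possibilities, and nothing assigns the Day 90 draw to the primary outcome. All of this stands. A reader might infer that the protocol prescribes 24 primary tests, each at 5%; the documents support only that 24 is the largest number compatible with their wording.

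Nor does any section say that one significant result would count as support, and the error rates above need that rule. This also stands, but the plan contains no rule that would prevent such a reading.

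It can also be said that the study is small and exploratory, and that 11.9 reports a detectable effect for a sample size already selected rather than a calculation for a stated hypothesis. The description of 11.9 is right. Even so, sections 11.3 and 11.4 state a hypothesis and a primary aim, and 11.9 attaches 80% power to a test. That is enough to require that the deciding comparison be identifiable.

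**Conclusion.** The point holds as a gap in specification: the primary comparison is undefined in strain, endpoint and visit, and there is no error control. The size is conditional. If any one significant result were taken as support, the false-positive chance would be about 27–50% for 24 tests, 20–30% for the 12 at Day 28, and 12–19% for the four Day 28 titre tests. Even the last of these is more than twice the nominal 5%, so the conclusion does not depend on the count of 24.

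A reader might take the middle value of about 40% as the trial's error rate. The documents do not support that. It rests on assumed correlations and titre levels, and 11.9 itself says that no preliminary data exist for the response rates. If the investigator intended one test pooled over strains at one visit, the rate would be 5%, but the plan does not say so.

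**What to change.** Before analysis, name in 11.5 one primary comparison (one endpoint, one visit, one rule across strains), tested once at two-sided 5%. Several choices are valid. One suitable example is the between-group difference in Day 28 log2 HI titre, averaged over the four strains and adjusted for the pre-vaccination titre.

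If that choice is made:

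- State which sample is baseline. The influenza antibody tube is drawn at Screening Visit #1, which the visit windows allow to fall up to about seven weeks before vaccination (2 weeks + 1 month + 1 week). The Day 0 pre-vaccine serum is closer in time but is listed under cytokines.
- Replace the t-test/Wilcoxon rule for the primary analysis with a test that adjusts for baseline, such as ANCOVA.
- Restate the detectable effect in 11.9, now given for a chi-square test, for the chosen primary.
- Report strain-specific Day 28 results as secondary with Holm correction over the four strains. Label Day 90, the other HI endpoints and neutralization as supportive.

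**Cost.** Sections 11.5 and 11.9 must be rewritten, including the test and the detectable effect. Results for single strains, for Day 90 or for the other endpoints can no longer be claimed as primary. No new visits, blood or participants are needed.
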